### **6.3 Surgery and Follow-up Visits**

#### ***Procedures at the time of surgery***

The following procedures will be performed on the day of surgery (before administration of anesthesia and before surgery):

- Record the patient's vital signs
- Obtain blood for routine laboratory tests
- Record all medications being taking, including prescription, over-the-counter, and herbal medications
- Discuss with the patient any new or unexpected changes they are feeling.
- Record any AEs.

Once the patient is under anesthesia, some procedures will occur that would not normally be part of surgery if the patient were not in this study. The SOC surgical procedures will be allowed to continue with the addition of the imaging steps listed below.

- If the primary tumor is not visually apparent using standard approaches, the NIR camera may be used to help locate and guide the resection of the primary tumor.
  - The primary tumor should be imaged prior to excision and following excision on a piece of normal tissue from a distance equal to the operating distance of the camera.
- If the primary tumor is apparent under standard conditions, it will be imaged prior to resection. Additionally, the resected tissue will be imaged using the

intraoperative camera on a section of normal tissue at a distance equal to the operating distance of the camera

- Following the primary tumor resection, margins (both on the excised primary and the affected lung) will be examined using NIR in an effort to detect residual disease
- All SOC lymph nodes to be collected during the operative procedure will be imaged prior to and following excision in a manner identical to the procedures used for imaging the primary resection
- Once the SOC primary tumor resection is complete, the surgeon will examine the thoracic cavity with the intraoperative NIR camera in search of additional fluorescent disease, or lymph nodes that were missed during SOC
- Additional fluorescent lesions, or lymph nodes will be imaged prior to excision, removed and imaged on a section of normal tissue in a manner analogous to the SOC specimens.
- For all resected specimens (including SOC primary tumor, margins, SOC lymph nodes and additional missed disease), fluorescence status and specimen name will be called out by the surgeon for documentation by the clinical research coordinator in the provided Imaging Workbook

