- Tumor Negative SOC Biopsies – during SOC surgery, the surgeon will collect tissue specimens that are suspicious for disease. If those samples do not demonstrate pegsitacianine fluorescence and are found to be devoid of tumor pathologically, those specimens would be included as a tumor negative SOC biopsy.
  - This occurs when any SOC sample (primary tumor, additional SOC specimen, or lymph node) that is collected is found to be negative for tumor, and did not fluoresce during *ex situ* imaging.

The number and proportion (with corresponding two-sided exact 95% confidence intervals) of subjects with any CSE will be reported.

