- Tumor Negative SOC Biopsies – during SOC surgery, the surgeon will collect tissue specimens that are suspicious for disease. If those samples do not demonstrate pegsitacianine fluorescence and are found to be devoid of tumor pathologically, those specimens would be included as a tumor negative SOC biopsy.
 - This occurs when any SOC sample (primary tumor, additional SOC specimen, or lymph node) that is collected that is found to be negative for tumor, and did not fluoresce during *ex situ* imaging.

A subject with any CSE will be considered a CSE responder.

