7.10.1 Primary Analyses

7.10.1.1 Analysis of Clinically Significant Events

The number and proportion of subjects with CSEs will be summarized by Part and overall. CSE responders will be summarized, as well as subjects with each type of CSE. These summaries will include 95% 2-sided confidence intervals for the proportion of CSEs calculated via Clopper-Pearson method.

A listing of all CSEs by patient will be provided.

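### The counting rule for the tumor-negative SOC biopsy event omits the suspicion condition in its own definition, so a non-suspicious, tumor-free, non-fluorescent lymph node can make a patient a primary-endpoint responder

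*SAP*

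**What the plan says.** SAP 5.1.1 describes the tumor-negative SOC biopsy CSE in two steps. The definition says that during SOC surgery "the surgeon will collect tissue specimens that are suspicious for disease". It then sets the condition for counting: "If those samples do not demonstrate pegsitacianine fluorescence and are found to be devoid of tumor pathologically". The samples referred to are the suspicious ones.

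The sub-bullet that states when the event occurs is wider. It counts "any SOC sample (primary tumor, additional SOC specimen, or lymph node) that is collected that is found to be negative for tumor". The only further condition is that the sample showed no fluorescence when imaged *ex situ*. It does not mention suspicion, and it names lymph nodes as eligible.

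Protocol 9.3 has the same definition and the same wider rule: "any SOC sample (primary tumor, additional SOC specimen, or lymph node) that is collected is found to be negative for tumor". The SAP's precedence over the protocol (SAP 1) therefore does not resolve the mismatch.

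The rule feeds the primary endpoint directly: "A subject with any CSE will be considered a CSE responder". SAP 7.10.1.1 reports both the composite and its parts: "CSE responders will be summarized, as well as subjects with each type of CSE".

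On which nodes are involved, Protocol 6.3 says "All SOC lymph nodes to be collected during the operative procedure will be imaged prior to and following excision". The design text (Protocol Summary, Protocol 3.1, SAP 3.1) applies the imaging procedure to any SOC node collected, then in the next sentence calls the removed nodes suspected. The specimen listing in SAP 7.10.2.1 gives specimen type, attainment by SOC or by fluorescence, pathology and fluorescence. It names no field for suspicion.

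**The concern.** The two texts give different numerators for the same event. A programmer will most likely code the sub-bullet. It is the explicit rule, the same unrestricted count is tabulated in SAP 7.9.5, and no listed variable would allow the definition to be applied.

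Under the sub-bullet, a lymph node that was never suspected, is tumor-free and does not fluoresce scores as a CSE. Under the definition it does not. Two reported results depend on which text is followed: the responder rate, and the separate rate for this CSE type. If SOC nodes are sometimes taken without suspicion, both rates will rise with the number of normal nodes removed, which reflects surgical practice more than the agent.

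Protocol 9.1 says the study is meant to inform power calculations for later trials. An ambiguous numerator would carry over into those calculations.

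**Working it through.** **Comparing the texts**

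| Condition | Definition | Counting rule |
|---|---|---|
| Tumor-free on pathology | required | required |
| Non-fluorescent | required | required (*ex situ*) |
| Suspicious to the surgeon | required | absent |
| Lymph nodes | only if suspicious | any SOC node |

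The two rules differ only for tumor-free, non-fluorescent SOC specimens that were not suspicious.

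**No plan figure to reproduce**

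The sample size of 40 rests on historical experience (Protocol 9.1, SAP 4). The documents give no expected CSE rate, precision target or node count.

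**Illustration of size**

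Inputs:
- k, tumor-free SOC nodes per patient: an assumption, shown for 1, 2, 3 and 5.
- s, the probability that such a node is non-fluorescent: an assumption. The value 0.70 is borrowed from the specificity threshold for opening Part 2, and 0.75 from the specificity reported for the first-in-human study (Protocol 1.2). Neither is a specificity for lung nodes. 0.50 is a low case.
- ρ, within-patient correlation: an assumption of 0, 0.3 or 0.5.

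With independent nodes, P(at least one dark node) = 1 − (1 − s)^k. For s = 0.70 and k = 3 this is 1 − 0.3³ = 1 − 0.027 = 97.3%.

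With correlation, a beta-binomial model has M = (1 − ρ)/ρ and b = (1 − s)M. For ρ = 0.3, M = 2.333 and b = 0.7. With k = 3, P(no dark node) = (0.7 × 1.7 × 2.7)/(2.333 × 3.333 × 4.333) = 3.213/33.70 = 0.095, so P(at least one) = 90.5%.

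| s, ρ | k = 1 | k = 2 | k = 3 | k = 5 |
|---|---|---|---|---|
| 0.70, 0 | 70.0% | 91.0% | 97.3% | 99.8% |
| 0.70, 0.3 | 70.0% | 84.7% | 90.5% | 95.1% |
| 0.70, 0.5 | 70.0% | 80.5% | 85.1% | 89.4% |
| 0.75, 0 | 75.0% | 93.8% | 98.4% | 99.9% |
| 0.50, 0 | 50.0% | 75.0% | 87.5% | 96.9% |

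If all 40 patients had three such nodes and s = 0.70, this route alone would give about 39 responders under independence (40 × 0.973 = 38.9; Clopper-Pearson interval for 39/40: 86.8% to 99.9%). At ρ = 0.3 it would give about 36 (40 × 0.905 = 36.2; interval for 36/40: 76.3% to 97.2%). The exact interval measures sampling error only and gives no sign that the numerator is ambiguous.

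**What these figures measure**

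They are the chance of at least one dark tumor-free node. They are not the difference between the two rules. For a given patient, the responder rate is inflated only if every such node was non-suspicious, no other suspicious SOC specimen was tumor-free and dark, and no other CSE type occurred. Under the stated assumptions, each table entry is therefore an upper bound on the inflation.

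**The case against.** The strongest counter-argument comes from the design text, which calls the removed nodes suspected in three places. No passage says that unsuspected nodes are taken. On that reading every SOC node is already suspicious, and the two rules give the same count for nodes. The definition's first sentence can also be read as describing SOC collection in general, with the sub-bullet then saying which SOC specimens count. The short statements of this CSE elsewhere (Protocol 2.1, SAP 2.1) carry no suspicion condition either.

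This stands in part. That unsuspected nodes are sampled is an inference, and the documents leave it open. But calling the nodes suspected is description and is not made a condition for counting. The same sections cover any SOC node, and Protocol 6.3 covers all of them. If every node is suspected, adding the condition changes no result; if not, it matters a good deal.

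A reader might infer more than the text supports:
- **Any tumor-free node makes a responder.** It does not, because the node must also be non-fluorescent. A tumor-free node that fluoresces is a false positive (SAP 5.1.2).
- **The 97% is the amount of inflation.** It is an upper bound under assumed inputs.
- **Under the definition these patients would contribute no event of this type.** That follows only if all their nodes are unsuspected and they have no other qualifying specimen.

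It is also fair to say that this is a pilot study without a formal hypothesis test or a success threshold for the CSE rate, and that reporting by CSE type already makes part of the problem visible. The type-specific row, however, has the same ambiguity as the composite.

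**Conclusion.** The mismatch is real, appears in both documents and affects the numerator of the primary endpoint. As written, the rule lets a non-suspicious, tumor-free, non-fluorescent SOC node make a patient a responder, which the definition directly above it does not.

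The size cannot be fixed from the documents. With three tumor-free nodes per patient and 70% node specificity, the upper bound on the inflation is 97% under independence and about 90% at correlation 0.3. All three inputs are assumptions. The true effect lies between zero, if every SOC node is suspicious, and that bound. The point should be settled before database lock because it is cheap to resolve and bears on the primary result. It does not affect the sample size, which rests on no calculation.

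**What to change.** Reconcile the two texts in SAP 5.1.1 and Protocol 9.3 so that the sub-bullet carries the suspicion condition of the definition: an SOC specimen taken because the surgeon judged it suspicious, found tumor-free, and non-fluorescent *ex situ*.

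Where data are still to be collected, add one yes/no field for suspicion to the Imaging Workbook, completed before any NIR imaging of that specimen. Recording it at call-out is too late, because Protocol 6.3 has SOC tumors and nodes imaged before excision and the call-out concerns resected specimens.

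SAP 3.1 already notes that Part 2 was not opened, so some data may exist without this field. Where suspicion was not recorded, report the CSE responder rate and the tumor-negative-biopsy row two ways, each with Clopper-Pearson intervals:
1. counting all SOC specimens;
2. excluding events that rest only on tumor-negative, non-fluorescent SOC lymph nodes.

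The specimen type and attainment fields in SAP 7.10.2.1 are enough for this. If the non-node SOC specimens were all suspicious, the rate under the definition lies between the two.

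Document the change as SAP 7.1 requires, including a protocol amendment if it may affect the primary conclusions, and update SAP 8 accordingly.

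The cost is wording in two documents, one extra field where still feasible, and one extra set of table rows. The second rate cannot exceed the first and will probably be lower, and the fallback may drop some nodes that were truly suspicious.

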5.1.2 Diagnostic Imaging Endpoints

Diagnostic performance of pegsitacianine will be assessed by calculating sensitivity, specificity, NPV, and PPV of pegsitacianine in detecting tumor containing tissue. The *ex situ* fluorescence status (any fluorescence vs. no fluorescence) of collected SOC and pegsitacianine guided specimens, as well as lymph nodes, will be compared to histological analyses of the collected specimens. Sensitivity and specificity for detecting tumor-containing tissue versus normal tissue

will be evaluated using tissue specimen fluorescence and the corresponding pathological outcomes.

True/false/negative/positive definitions are as follows:

- False positive is defined as fluorescence was observed on the sample but the sample was not found to have tumor via pathology.
- False negative is defined as no fluorescence was observed on the sample but the sample was found to have tumor via pathology.
- True positive is defined as fluorescence was observed on the sample and the sample was found to have tumor via pathology
- True negative is defined as no fluorescence was observed on the sample and the sample was found not to have tumor via pathology.

Pegsitaricaine sensitivity and PPV will be calculated using the following equations:

$$\text{Sensitivity} = \frac{\text{\# of True Positive Specimens}}{\text{\# of True Positive Specimens} + \text{\# of False Negative Specimens}}$$

$$PPV = \frac{\# \text{ of True Positive Specimens}}{\# \text{ of True Positive Specimens} + \# \text{ of False Positive Specimens}}$$

Pegsiraniline specificity values and NPV will be calculated using the following equations:

$$\text{Specificity} = \frac{\text{\# of True Negative Specimens}}{\text{\# of True Negative Specimens} + \text{\# of False Positive Specimens}}$$

$$NPV = \frac{\# \text{ of True Negative Specimens}}{\# \text{ of True Negative Specimens} + \# \text{ of False Negative Specimens}}$$

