#### 9.4 Imaging Analysis

Diagnostic performance of pegsitacianine will be assessed at the level of the specimen by calculating the *ex situ* sensitivity, specificity, PPV, and NPV of pegsitacianine in detecting tumor containing tissue. The *ex situ* fluorescence status of collected SOC and pegsitacianine guided specimens will be compared to the histological analyses of the collected specimens (which is used to determine each sample's status as true/false positive/negative). For determining these operating characteristics, consider the following definitions:

- False positive is defined as “fluorescence was observed on the specimen but the specimen was not found to have tumor via histological analysis”.
- False negative is defined as “no fluorescence was observed on the specimen but the specimen was found to have tumor via histological analysis”.
- True positive is defined as “fluorescence was observed on the specimen and the specimen was found to have tumor via histological analysis”.
- True negative is defined as “no fluorescence was observed on the specimen and the specimen was found not to have tumor via histological analysis”.

The number of specimens in each category (each combination of true/false positive/negative), along with the true/false positive/negative rates (and corresponding exact two-sided 95% confidence intervals) will be reported. These rates will be used to determine pegsitacianine's tumor detection sensitivity, specificity, PPV, and NPV using the following equations:

$$\text{Sensitivity} = \frac{\# \text{ of True Positive Specimens}}{\# \text{ of True Positive Specimens} + \# \text{ of False Negative Specimens}}$$

$$\text{Specificity} = \frac{\# \text{ of True Negative Specimens}}{\# \text{ of True Negative Specimens} + \# \text{ of False Positive Specimens}}$$

$$\text{PPV} = \frac{\# \text{ of True Positive Specimens}}{\# \text{ of True Positive Specimens} + \# \text{ of False Positive Specimens}}$$

$$\text{NPV} = \frac{\# \text{ of True Negative Specimens}}{\# \text{ of True Negative Specimens} + \# \text{ of False Negative Specimens}}$$

These rates will be reported along with exact two-sided 95% confidence intervals.

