If the primary tumor is located using standard white light procedures, the tumor will be imaged using the NIR camera and removed as per standard of care (i.e., wedge, lobectomy, etc.). The primary resection will then be imaged (front, back and margins) on a piece of normal tissue within the surgical field at a distance from the specimen equal to the working distance of the camera system. Inspection and imaging of the resection margins will be performed using the NIR camera system. If an area of suspicion is observed, images will be captured of the area, at the working distance of the camera away from the margin and documented for future correlation to pathological findings. Similarly, the *in situ* resection margin on the lung will be imaged for signs or residual fluorescence that may correspond to disease left behind. If found, images will be captured prior to the excision of the margin (*in situ*) and following its resection on a piece of normal tissue (*ex situ*). Resection of the suspicious or fluorescent margin is at the discretion of the surgeon. This procedure is to be repeated if additional SOC nodules are planned for resection. An identical approach will be followed for any SOC lymph nodes collected during the procedure. Lymph node imaging will occur prior to and following the removal of the suspected lymph nodes.

Once SOC surgical resection is complete, the surgeon will use the NIR camera system to evaluate the thoracic cavity (i.e., chest wall, contralateral lung, bronchi, etc.) for indications of residual fluorescence. If additional fluorescent foci are observed, the area may be resected, at the discretion of the surgeon, for pathological confirmation of disease. Similar to the imaging of margin resections, the suspected area will be imaged prior to removal (*in situ*) and following resection (*ex situ*) on a piece of normal tissue within the thoracic cavity. Additional fluorescent lymph nodes, detected during the evaluation of the thoracic cavity, may also be collected and imaged both *in situ* and *ex situ* prior to being evaluated in pathology. Thus, each subject is their own "intrapatient" control.

Collected surgical specimens will be documented as called out by the surgeon. The fluorescence status of each specimen will then be correlated to the final pathology for each and the performance metrics of pegasitacianine will be tabulated.

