5. ANALYSIS ENDPOINTS

5.1 Efficacy Endpoints

5.1.1 Clinically Significant Event Endpoints

Performance metrics will include the identification of a CSE detected by pegasitacianine. CSEs will include pegasitacianine detection of primary tumors otherwise undetectable using SOC procedures, detection of occult disease not otherwise known by the surgeon to exist (as synchronous disease), the detection of a positive surgical margin, and accurate identification of tumor negative SOC biopsies. A list of CSEs and their definitions is provided below.

- **Detection of Synchronous Disease** – identification of tumor-containing tissue due to pegasitacianine fluorescence, confirmed via histopathological analysis, that otherwise went undetected during pre-operative imaging (PET, CT, MRI) or by the surgeon during SOC surgery.
 - This occurs when a specimen that comes from the thoracic cavity or lymph nodes, is (1) collected via fluorescence and (2) is pathologically-confirmed as a tumor. Note that any specimen collected from the thoracic cavity following SOC will be considered to be collected by fluorescence.

- Detection of Positive Surgical Margin – following the completion of SOC surgery, the surgical fields will be examined for residual fluorescence. Detection of a positive surgical margin would be those specimens collected as a result of residual pegsitacianine fluorescence following the completion of SOC surgery that return a histologically positive for tumor outcome.
 - This occurs when a margin specimen (either from the primary tumor or a lung resection margin) (1) is collected via fluorescence and (2) is pathologically-confirmed as a tumor. Note that any lung resection margin collected will be considered to be collected by fluorescence.
- Identification/Localization of the Primary Tumor – during SOC surgery, the surgeon will examine the affected lung to locate the primary tumor. If the primary tumor is not visually apparent using standard imaging methods the surgeon may use the NIR imaging device to aid in localization. If the NIR imaging identifies and/or locates the primary tumor, which was undetectable using SOC approaches, this will be deemed a CSE.
 - This occurs when the primary tumor is not located using SOC approaches, and is instead identified using NIR imaging.

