7.10.2 Secondary Analyses

7.10.2.1 Analysis of Diagnostic Imaging

The positive predictive value, negative predictive value, sensitivity, and specificity (specimen level) will be calculated and summarized for each Part and overall. The summary will include the true/false negative/positive rate and number of specimens. Two-sided 95% confidence intervals will be calculated for each rate via Clopper-Pearson method.

A listing by subject and specimen showing the specimen type (primary tumor/ additional SOC specimen, lung resection margin, thoracic cavity, lymph node), attainment by SOC or fluorescence (if primary/ additional SOC/ lymph), pathology result, fluorescence *in situ* and *ex situ*, and fluorescence measures (MFI and TBR) will be provided.

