7.10.3.2 ROC Analysis

In this pilot study we are assuming that any fluorescence is indicative of tumor presence. To assess how the amount of observed fluorescence (e.g., the SBR or TBR) may affect the diagnostic accuracy of pegasitacianine, a receiver operating characteristic (ROC) analysis will be performed on all specimens using the observed thresholds of SBR and TBR. The corresponding ROC curve

will be provided along with the area under the curve (AUC) and the 95% confidence interval of the AUC.

There is potential for within-subject correlation to bias our estimates of pegsitacianine's diagnostic accuracy. To assess this issue, an ROC curve will be constructed from a mixed model that clusters specimens by the subject they originated from. We will compare the AUC of the mixed effects ROC curve to the standard ROC curve to assess if within-subject correlation is causing significant bias in our analyses. If it is determined that significant bias has been introduced, additional analyses on secondary endpoints may be performed to assess the diagnostic accuracy of pegsitacianine.

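### Sensitivity and specificity pool standard-of-care specimens with fluorescence-guided ones, so pooled specificity depends on how many benign guided foci are resected; add an estimate on the standard-of-care set

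*SAP*

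**What the plan says.** SAP 5.1.2 defines sensitivity, specificity, PPV and NPV from ex situ fluorescence (any versus none) "of collected SOC and pegsitacianine guided specimens, as well as lymph nodes, will be compared to histological analyses of the collected specimens". Protocol 9.4 uses the same pool: the ex situ "fluorescence status of collected SOC and pegsitacianine guided specimens will be compared to the histological analyses of the collected specimens".

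The specimens reach this table by two routes:

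- **SOC specimens** (primary tumor, additional SOC specimens, SOC lymph nodes) are taken on standard surgical grounds and imaged whether or not they fluoresce.
- **Guided specimens** follow from the NIR inspection. SAP 3.1 says of the cavity: "If additional fluorescent foci are observed, the area may be resected, at the discretion of the surgeon, for pathological confirmation of disease". Of margins it says: "Resection of the suspicious or fluorescent margin is at the discretion of the surgeon". Extra fluorescent nodes may also be collected.

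SAP 5.1.1 fixes how two specimen types are classified: "Note that any specimen collected from the thoracic cavity following SOC will be considered to be collected by fluorescence", and "Note that any lung resection margin collected will be considered to be collected by fluorescence".

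SAP 7.10.2.1 summarizes the four metrics by Part and overall, with Clopper-Pearson intervals. Whether a primary, additional SOC or nodal specimen was obtained by SOC or by fluorescence appears in the accompanying specimen listing. SAP 7.9.5 separately tabulates the fluorescent areas removed by site, and the additional areas found by NIR after SOC and confirmed as cancer. No section plans sensitivity or specificity by route of collection.

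**The concern.** A specimen taken because it fluoresced has been selected on the test under evaluation. If it still fluoresces on re-imaging after excision, it can only be a true or a false positive. Non-fluorescent cavity and margin tissue beyond SOC is not planned for collection, so nothing from those sites supplies the balancing negatives. Each benign guided focus that stays fluorescent adds one to the specificity denominator and nothing to its numerator. Two surgeons using the same agent in the same patients could then report different specificities because one explored further.

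Sensitivity, specificity, PPV and NPV are secondary endpoints (SAP Table 1), and Protocol 9.1 gives the study's goal as informing power calculations for later studies. A specificity that partly reflects resection habits is a poor input for that purpose.

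The other planned analyses do not address this. The mixed-model ROC check (SAP 7.10.3.2) concerns within-subject correlation. The Breslow-Day test (SAP 7.10.3.3) concerns camera system. The optional covariates in SAP 7.10.3.4 do not name route of collection.

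**Working it through.** **Inputs.** The documents give no expected number of SOC or guided specimens, no malignant share and no rate of ex situ persistence, so there is no planned figure to reproduce. The formulas are those of SAP 5.1.2; every count below is an assumption.

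- SOC set: D = 60 specimens with tumor, of which 48 fluoresce (80%); H = 100 without tumor, of which 80 do not (80%).
- G guided specimens: 10, 20 or 40.
- f, the share of guided specimens with tumor: 20 to 40%.
- q, the share of guided specimens still fluorescent ex situ: 80 to 100%.

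**Formulas.**

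Pooled specificity = (80 + (1 − q)(1 − f)G) / (100 + (1 − f)G)

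Pooled sensitivity = (48 + q·f·G) / (60 + f·G)

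**Specificity** (SOC set alone: 80/100 = 80%).

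| G | Lowest (f = 20%, q = 100%) | Highest (f = 40%, q = 80%) |
|---|---|---|
| 10 | 80/108 = 74.1% | 81.2/106 = 76.6% |
| 20 | 80/116 = 69.0% | 82.4/112 = 73.6% |
| 40 | 80/132 = 60.6% | 84.8/124 = 68.4% |

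**Sensitivity** (SOC set alone: 48/60 = 80%).

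- q = 100%, f = 40%: 52/64 = 81.3% (G = 10), 56/68 = 82.4% (G = 20), 64/76 = 84.2% (G = 40).
- q = 80%: no change at any G, because persistence equals SOC sensitivity. For example, with G = 20 and f = 40%, (48 + 6.4)/68 = 80.0%.

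**A higher starting point.** With 90% for both (54/60 and 90/100) and G = 20, specificity runs from 90/116 = 77.6% to 92.4/112 = 82.5%. Sensitivity with f = 40% is (54 + 8)/68 = 91.2% at q = 100% and (54 + 6.4)/68 = 88.8% at q = 80%. It can therefore fall as well as rise.

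**When the dependence disappears.** Pooled specificity is unaffected only if benign guided tissue fluoresces ex situ at 1 minus SOC specificity, which is 20% in the first scenario. Check with G = 20, f = 20%, so 16 benign guided specimens: (80 + 0.8 × 16)/116 = 92.8/116 = 80.0%. Pooled sensitivity is unaffected when persistence in malignant guided tissue equals SOC sensitivity.

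**NPV.** With q = 100%, guided specimens add no negatives, and NPV stays at 80/(80 + 12) = 87.0%. With G = 20, f = 40% and q = 80% it is 82.4/(82.4 + 13.6) = 85.8%.

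**A second assumed set.** With 40 tumor specimens (26 fluorescent) and 80 benign (60 not fluorescent), the SOC values are 65.0% (95% CI 48.3 to 79.4) and 75.0% (64.1 to 84.0). Adding 40 guided specimens, half with tumor, 80% persistent, gives sensitivity (26 + 16)/60 = 70.0% and specificity (60 + 4)/100 = 64.0%.

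**The case against.** Several points count against a stronger reading, and most of them stand.

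- **Selection is in situ but scoring is ex situ.** A guided specimen can be scored negative. This weakens the effect. It removes the effect on specificity only if benign guided foci fluoresce after excision no more often than benign SOC tissue, which is hard to expect of tissue picked for fluorescing.
- **A reader might infer that sensitivity is inflated.** The documents do not support a fixed direction. The shift depends on persistence relative to SOC sensitivity and can be zero or negative. The one earlier sensitivity shown, 100% in ON-1001 (Protocol 1.2, other tumor types), could not be raised by pooling.
- **A reader might infer that non-fluorescent tissue is never sampled and that every guided specimen fluoresced.** SOC lymph nodes are collected and imaged regardless of fluorescence, so nodes do supply negatives. SAP 3.1 also allows resection of a margin that is merely suspicious, and the SAP 5.1.1 notes are classification rules rather than evidence about each specimen.
- **A reader might infer that guided yield goes unreported.** SAP 7.9.5 already plans much of it. What is missing is an accuracy estimate by route.
- **A reader might infer that study decisions are at risk.** Protocol 9.8 makes the interim review optional and says it rests on no individual endpoint. The 70% criterion for opening Part 2 has no remaining role, because SAP 3.1 records that Part 2 was not opened.
- **An SOC-only set can carry its own bias.** Dropping primaries located by NIR would again select on the test: those found by fluorescence would leave, while non-fluorescent ones resected later would stay as false negatives. They must be kept. SOC tissue is also chosen on suspicion, so this set does not isolate the agent perfectly, and it cannot count non-fluorescent disease left behind.

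**Conclusion.** The concern holds for pooled specificity, as a structural feature of the planned table. Specificity falls with each benign guided focus that stays fluorescent ex situ, and no planned analysis shows by how much. Sensitivity moves less under the first two assumed scenarios, and its direction is not fixed.

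The size cannot be known from the documents. In the 80%/80% scenario, 20 guided specimens move specificity from 80% to between 69% and 74%, and sensitivity from 80% to between 80% and 82%. If few foci are resected, or few benign ones persist ex situ, the shift will be small.

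The harm is confined to the reported secondary endpoints and their reuse in planning later studies. The primary endpoint, the proportion of subjects with a clinically significant event, is not calculated from this table. This is an inexpensive improvement to interpretation; it does not make the prespecified analysis invalid.

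**What to change.** In SAP 5.1.2 and 7.10.2.1, and in Protocol 9.4:

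1. Add sensitivity, specificity and NPV on an SOC set, defined as all primary tumors (including those located by NIR), additional SOC specimens and SOC lymph nodes. Use this set when interpreting the agent's accuracy.
2. Report PPV (the share with tumor) separately for guided margins, cavity specimens and extra lymph nodes, building on the counts already planned in SAP 7.9.5.
3. Keep the pooled table as prespecified, with a note that its values depend on how many guided specimens were resected.

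No new data are needed. The SAP 7.10.2.1 listing holds specimen type, route, pathology and ex situ status, and SAP 5.1.1 assigns cavity and lung-margin specimens by rule. SAP 7.1 allows changes to the statistical methods before database lock.

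The cost is one extra table and slightly wider intervals from fewer specimens. For sensitivity in the 80%/80% scenario, the Clopper-Pearson 95% interval is 67.7 to 89.2% on the SOC set (48/60), against 71.2 to 90.5% pooled (56/68; G = 20, f = 40%, q = 100%).
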